PCT is a manualized evidenced-based PTSD treatment (Frost et al., 2014) used in several large-scale PTSD trials (e.g., Schnurr et al., 2007). It incorporates the essential therapeutic elements common to different types of psychotherapies, including supportive empathic listening and unconditional positive regard. The therapist plays an active role but does not impart any systematic training. The focus is to create an understanding of how the symptoms of PTSD are related to day-to-day difficulties and to help patients develop new, more adaptive responses to these stressors with a problem-focused and problem-solving approach. PCT includes weekly homework assignments. These include reading psychoeducational handouts and self-monitoring problems and stressors in a daily diary, which are then problem-solved in session. In prior trials, PCT showed equivalent change to active therapies at the last follow-up. The VA offers PCT as an evidence-based therapy for PTSD. So, this design element represents a conservative test of the superiority of AD-MIL.

Participants in both treatment arms will receive 12 weekly 90-minute sessions of individual psychotherapy.

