#### *Data Safety Monitoring Board (DSMB), Adverse Events (AE), Unanticipated Problems Involving Risk (UPR), and Protocol Deviations*

**Data Safety Monitoring Board (DSMB):** A DSMB has been created for the study, including Drs. [name], [name], and [name] at the VA Boston Healthcare System. The DSMB is tasked with independently ensuring the safety of study participants and scientific goals. The DSMB will review the initial protocol and any proposed amendments, meet and complete reports bi-yearly, perform expedited monitoring of all serious adverse events, perform ongoing monitoring of drop-outs and non-serious adverse events, determine whether study procedures should be changed or the study should be halted for reasons related to the safety of study subjects, and perform periodic review of the completeness and validity of data to be used for analysis of safety and efficacy. The DSMB will also ensure subject privacy and research data confidentiality. A statistical

penalty will not be assessed for the ongoing unblended review of safety by the DSMB. Unblinded data will not be released to investigators unless necessary for safety reasons. Suspected information security and privacy incidents will be reported within one hour to the Information Security and Privacy Officers and Research Administration.

**Adverse Event (AE):** An adverse event (AE) is any untoward physical or psychological occurrence directly or indirectly affecting a human subject participating in research.

Adverse Event is a broad term covering physical, psychological, social, legal or economic occurrence directly or indirectly affecting a human subject participating in research. An AE can be any unfavorable or unintended event including abnormal laboratory finding, symptom or disease associated with the research or the use of a medical investigational test article (includes drug, biologic, or device). An AE may or may not have a causal relationship with the research, or any risk associated with the research or the research intervention, or the assessment. Adverse events involve participants only.

Negative events that are **unanticipated and unrelated** (by reasonable judgment) will be logged and tracked over the course of the study and reported in a summary of their occurrence at DSMB bi-yearly meetings, as well as for continuing reviews and at end of study. Examples might include medical problems, legal problems, homelessness, or traumatic events.

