The therapist will query about adverse events (AEs) at every session by asking about any notable events since the last visit. These will be reviewed in a timely manner with the supervisor.

**Serious Adverse Event (SAE):** A SAE occurring in a patient or subject enrolled in a research study is serious if it results in any of the following outcomes: death, a life-threatening adverse drug experience, inpatient hospitalization or prolongation of existing hospitalization, a persistent or significant disability/incapacity, or is a congenital anomaly/birth defect. This will be reported to the IRB within 5 business days, as stated in reporting requirements. The only exception is death, which requires immediate reporting.

**Unanticipated Problems Involving Risk (UPR):** Defined as being (1) unexpected given the research procedures and characteristics of the population, (2) related (or possibly related) to participation in the research and (3) indicative that the research may place the subject or others at a greater risk of harm than was previously known. UPRs require notifying the IRB immediately.

Examples of possible UPRs for psychotherapeutic interventions:

1. Psychosis or mania
2. New onset or clinically significant exacerbation of a psychiatric disorder
3. Suicide and suicide attempts

An incident, experience, or outcome that meets UPR criteria generally will warrant consideration of substantive changes in the research protocol or informed consent process/document or other corrective actions in order to protect the safety, welfare, or rights of subjects or others. Examples of corrective actions or substantive changes that might need to be considered in response to an unanticipated problem include:

- \* modification of inclusion or exclusion criteria to mitigate the newly identified risks;
- \* implementation of additional procedures for monitoring subjects;
- \* suspension of enrollment of new subjects;

- \* suspension of research procedures in currently enrolled subjects;
- \* modification of informed consent documents to include a description of newly recognized risks; and
- \* provision of additional information about newly recognized risks to previously enrolled subjects.

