## **Reporting Requirements:**

**UPR:** Immediately notify IRB

**SAE:** Report to IRB within 5 business days

**AE that is unanticipated and unrelated:** Track in AE Log (summary will be reported quarterly to DSMB and as needed)

**All other AEs:** Report to IRB within 10 business days

To report to the IRB, an AE form, SAE form, and/or UPR form will be completed, the site PI's signature will be obtained, and the form will be submitted to the local IRB. The form (with encryption) will be emailed to the Study Coordinator. The Coordinator will forward each completed AE/SAE/UPR form to Data Safety Monitoring Board as soon as possible and will maintain a record of all AEs/SAEs/UPRs (see AE Log) to report to the Boston IRB in summary or table form at the time of annual Continuing Review. In the case that a Boston IE learns of an AE/SAE/UPR during the course of a telephone contact, the IE will initiate the AE/SAE/UPR Form and email (with encryption) to the local PI at the site where the participant was recruited (i.e., [name]: Minneapolis, [name]: San Diego, [name]: San Francisco, or [name]: Central Texas) for signature and submission to the local IRB (i.e., the site at which the participant was seen). The Study Coordinator will notify RR&D of any UPR, AE, or SAE promptly via encrypted email.

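### The life-threatening SAE item covers only drug experiences in a psychotherapy trial, and the log-only reporting row is not limited to non-serious events

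*Combined protocol and SAP*

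**What the plan says.** All references are to the Combined protocol and SAP.

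- **Treatment Arms.** "Participants in both treatment arms will receive 12 weekly 90-minute sessions of individual psychotherapy". No study drug is described.
- **SAE definition** (in the section on the DSMB, AEs, UPRs and deviations). An event is serious if it results in "death, a life-threatening adverse drug experience, inpatient hospitalization or prolongation of existing hospitalization, a persistent or significant disability/incapacity", or in a congenital anomaly. On timing: "This will be reported to the IRB within 5 business days, as stated in reporting requirements". The next sentence reads "The only exception is death, which requires immediate reporting".
- **UPR definition** (same section). Three conditions must all hold: the event is unexpected, it is at least possibly related to the research, and it points to more risk than was known. The list of possible UPRs for psychotherapy includes "Suicide and suicide attempts".
- **AE definition** (same section). Events judged unanticipated and unrelated "will be logged and tracked over the course of the study and reported in a summary of their occurrence at DSMB bi-yearly meetings".
- **Reporting Requirements.** There are four rows. A UPR goes to the IRB immediately. For an SAE the row says "Report to IRB within 5 business days". For an unanticipated and unrelated AE it says "Track in AE Log (summary will be reported quarterly to DSMB and as needed". All other AEs go to the IRB in 10 business days.
- **DSMB paragraph.** The board gives SAEs expedited monitoring and follows non-serious events on an ongoing basis.

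**The concern.** Whether an event is serious is normally settled by its outcome. Here one outcome, threat to life, counts only when it comes from a drug experience. The item is not quite empty, since a reaction to a participant's own medication could meet it. It does not reach events that arise from the therapy or from the illness under treatment, which are the ones this trial needs to catch.

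Suicidality matters in this population by the plan's own account: it appears among the exclusions, the eligibility interview modules and the exploratory outcomes. If a life-threatening attempt is not an SAE, it loses its claim to expedited DSMB monitoring, and its handling then depends on judgements of expectedness and relatedness. On one branch of those judgements, the reporting list asks only for a log entry and a periodic summary.

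The same log-only row raises a second problem. Nothing in it excludes serious events, so a hospital admission can carry two different instructions.

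**Working it through.** The plan gives no figure to reproduce, so the check applies the written rules to one event, a non-fatal suicide attempt. One assumption is needed: unanticipated (AE definition and Reporting Requirements) means the same as unexpected (UPR definition).

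**Step 1. Is it an SAE?** Suppose there is no admission and no lasting disability. It is not a death, an admission, a disability or a congenital anomaly. The life-threatening item requires a drug experience. Literally, the attempt is not an SAE, however close to fatal it was.

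**Step 2. Which row applies?** The three UPR judgements give 2 × 2 × 2 = 8 combinations. Adding whether there was admission or disability gives 16.

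| Unexpected | Related | Greater risk | No admission or disability | Admission or disability |
|---|---|---|---|---|
| yes | yes | yes | UPR, immediate | UPR, immediate, and SAE, 5 days |
| yes | yes | no | other AE, 10 days | SAE, 5 days |
| yes | no | yes | log only | SAE, 5 days, and log |
| yes | no | no | log only | SAE, 5 days, and log |
| no | yes | yes | other AE, 10 days | SAE, 5 days |
| no | yes | no | other AE, 10 days | SAE, 5 days |
| no | no | yes | other AE, 10 days | SAE, 5 days |
| no | no | no | other AE, 10 days | SAE, 5 days |

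(Days are business days.)

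- Without admission or disability: 1 UPR + 5 other AE + 2 log only = 8. That is three routes, none of them the 5-day route.
- With admission or disability: 1 UPR and SAE + 5 SAE + 2 SAE and log = 8. The UPR-and-SAE cell causes no difficulty, because meeting the earlier clock meets both. The 2 SAE-and-log cells carry conflicting instructions, and no rule says which prevails.

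These are counts of logical cells, not of expected events. Some cells, such as unrelated with greater research risk, would be rare.

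**Step 3. What does the DSMB receive?** Reporting Requirements has the coordinator send each completed AE, SAE or UPR form to the DSMB without delay. Those forms are the ones completed for reporting to the IRB. An attempt on the UPR or 10-day route therefore reaches the board. For a logged event, the list prescribes a summary and not an individual report.

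**Step 4. Does the word drug change the result?** Let the item cover any cause, and suppose the attempt is judged life-threatening. The 16 cells become 2 UPR and SAE, 10 SAE, and 4 SAE and log. The 10-day and log-only results disappear, so the word does change the result. The 4 overlaps remain until the log-only row is limited to non-serious events. With that second edit the count is 2 UPR and SAE, and 10 + 4 = 14 SAE.

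**Step 5. The two smaller mismatches.**

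- Death: the SAE definition makes it an immediate-report exception to the 5-day rule. The SAE row in Reporting Requirements, which that definition cites, does not repeat the exception.
- DSMB summary of logged events: at bi-yearly meetings in the AE definition, quarterly in Reporting Requirements. If bi-yearly means twice a year, the intervals are about 6 and about 3 months.

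**The case against.** The best defence is that the scheme is tiered and mostly works. Different facts lead to different clocks, as they should, and judging relatedness and expectedness is part of any UPR definition. That stands. The drug wording is a gap inside one definition, and the reporting list does not contradict it.

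The log-only route for an attempt can also be called strained. The plan's log examples are things like legal trouble or homelessness, suicide attempts are named as possible UPRs, and a possible relation is enough for that criterion. If the example list alone made every attempt a UPR, all 16 cells would carry immediate notification. But the list is of possible UPRs and the three conditions still apply, so the text leaves the log-only route open. The log-only row does add reporting as needed, and RR&D is to be told promptly of AEs. These reduce the exposure, but neither supplies an SAE label or an individual IRB report.

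A reader might infer more than the documents support:

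- *That an attempt without admission also has a 5-day route.* It has one only if a site disregards the word drug, which departs from the text.
- *That the DSMB would not hear of an attempt lacking the SAE label.* The form-forwarding rule says otherwise, except on the log-only route.
- *That the plan sets two rival clocks for death.* The SAE definition states a rule with an express exception, and the short list omits it. This is an omission to repair.
- *That comparisons of SAE counts between arms would be biased.* The Analyses section plans no such comparison, and a central record of all events is kept.

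The AE, SAE and UPR forms and the AE Log are not in the documents. They may record seriousness separately, and this cannot be judged here.

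**Conclusion.** Wrong as written, of moderate severity. Two defects follow from the text alone. The SAE definition leaves out life-threatening events that are not drug experiences and meet no other listed outcome. The log-only row overlaps the SAE row for events judged unanticipated and unrelated, with no precedence rule. In the check, 2 of 8 cells for an attempt without admission or disability end in a log entry only, and 2 of 8 with admission or disability carry conflicting instructions. The death exception and the summary frequency are lesser mismatches of wording.

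The conclusion rests on reading the rules literally and on treating unanticipated and unexpected as one term. A sensible site might well report more than the rules require, but the rules do not oblige it to. No sample size, power or efficacy analysis is affected.

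**What to change.** 1. In the SAE definition, replace the drug wording with life-threatening adverse event.
2. State that seriousness is classified first, before relatedness and expectedness, so that the log-only and 10-day rows of Reporting Requirements cover only non-serious events.
3. Reconcile the timing of death reports between the SAE definition and Reporting Requirements.
4. Reconcile the frequency of DSMB summaries between the AE definition and Reporting Requirements.

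The sponsor chooses the clocks; what is needed is that the sections agree. There is no need to declare every suicide attempt an SAE by name. Items 1 and 2 are enough to classify those that threaten life.

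The cost is a wording amendment, a check that the event forms match it, and a few more SAE reports.

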## **Reporting Requirements:**

**UPR:** Immediately notify IRB

**SAE:** Report to IRB within 5 business days

**AE that is unanticipated and unrelated:** Track in AE Log (summary will be reported quarterly to DSMB and as needed)

**All other AEs:** Report to IRB within 10 business days

To report to the IRB, an AE form, SAE form, and/or UPR form will be completed, the site PI's signature will be obtained, and the form will be submitted to the local IRB. The form (with encryption) will be emailed to the Study Coordinator. The Coordinator will forward each completed AE/SAE/UPR form to Data Safety Monitoring Board as soon as possible and will maintain a record of all AEs/SAEs/UPRs (see AE Log) to report to the Boston IRB in summary or table form at the time of annual Continuing Review. In the case that a Boston IE learns of an AE/SAE/UPR during the course of a telephone contact, the IE will initiate the AE/SAE/UPR Form and email (with encryption) to the local PI at the site where the participant was recruited (i.e., [name]: Minneapolis, [name]: San Diego, [name]: San Francisco, or [name]: Central Texas) for signature and submission to the local IRB (i.e., the site at which the participant was seen). The Study Coordinator will notify RR&D of any UPR, AE, or SAE promptly via encrypted email.

## **Protocol Deviation/Violation**

A protocol deviation or violation is any change, divergence, or departure from the study design or procedures of a research protocol. Investigators are required to conduct their research according to the plans reviewed and approved by the IRB. Instances where this does not occur, either inadvertently due to circumstances beyond the investigator's control, or due to errors of omission or commission by research project staff, must be reported.

Reporting Requirement: Fill out a Protocol Deviation/Violation form, and submit to local IRB within 3 days of the occurrence (one day if there was harm to the participant). Also email the form (with encryption) to the PI and Study Coordinator, who will maintain a record of all Protocol Deviations/Violations to report to the Boston IRB at the time of annual Continuing Review.

## *Measures*

Eligibility will be determined by scores on the CAPS-5 (Weathers et al, 2013) and select modules of the Mini International Neuropsychiatric Interview (e.g., Manic and Hypomanic Episodes, Alcohol Use Disorder, Substance Use Disorder, Psychotic Disorders and Mood Disorder with Psychotic Features, Suicidality, Homicidality; MINI; Sheehan et al, 2015). In addition, potential participants will be queried about current mental health treatment (i.e. Mental Health Service History form) to determine eligibility.

The **Moral Injury Events Scale (MIES;** Nash et al., 2013) is an 9-item scale that evaluates various military-related potential moral transgressions by self or others. The MIES has good internal and temporal consistency, and good discriminant and concurrent validity (Nash et al., 2013).

The **Working Alliance Inventory (WAI; Horvath & Greenberg, 1989)** assesses the quality of the working relationship between therapist and client. This working relationship, or alliance, is comprised of three components: the bond between therapist and client, shared goals, and engagement in relevant tasks in sessions. The WAI can be completed by both the therapist and the client. The original version contained 36 items, but a 12-item short-form was developed (WAI-S; Tracey & Kototovic, 1989), which displayed similarly good psychometric properties as the full-length WAI (Busseri & Tyler, 2003). The WAI-S is used in the current study.

The **Deployment Risk and Resiliency Inventory-2 (DRRI-2; Vogt et al., 2013)** **Combat Experiences and Aftermath of Battle** subscales, military service and **demographics** questionnaires, and the **DVBIC TBI Screening Instrument, and Montreal Cognitive Assessment (MoCA; Nasreddine, 2017)** will be administered at baseline only.

#### **A. Functional and behavioral change hypotheses**

Hypothesis A.1.

**Sheehan Disability Scale (SDS; Sheehan, 1983; Sheehan et al., 1996).** The SDS will be our primary functional outcome measure. Respondents indicate the degree to which symptoms disrupted work/school, social life, and family life/responsibilities on an 11-point scale ranging from “Not at all” to “Extremely,” and list the number of lost and unproductive work or school days. For this study, we will have participants’ index impairment caused by *PTSD symptoms* in the last month. The SDS is widely used to track disability in clinical trials and has demonstrated very good criterion (change from treatment) validity (Sheehan & Sheehan, 2008). We will use a prorated total mean score for the dimensional ratings such that only social and family ratings will be included for veterans who were not employed or attending school.

Hypothesis A.2.

**Brief Inventory of Psychosocial Functioning (B-IPF; Marx 2013).** Overall psychosocial functioning will also be assessed with this 7-item scale indexing overall level of functioning in seven life domains: romantic relationship, relationship with children, family relationships, friendships and socializing, work, training and education, and activities of daily living. Respondents indicate the degree to which they had trouble in the last 30 days in each area on a 7-point scale ranging from “Not at all” to “Very much.” The B-IPF has demonstrated concurrent validity, and the full 80-item IPF from which it was created has strong test-retest reliability and internal consistency (Marx, 2013). This scale is regularly used in PTSD clinical team settings in the VA.

**DRRI-2 (Vogt et al., 2013).** The **Post-Deployment Social Support** subscale of the DRRI will be used to assess social support resources. This subscale has excellent psychometric properties.

Hypothesis A.3.

**The CAIR Pandemic Impact Questionnaire (C-PIQ; MacLean & Cloitre, 2020).** We will measure COVID-related stress with the C-PIQ, a 19-item scale that measures COVID-19 exposure and the psychological impact of the pandemic. The C-PIQ has good psychometric properties (Lang, 2020, adapted from MacLean & Cloitre, 2020).

## B. Mental health change hypotheses

Hypothesis B.4.

**Clinician-Administered PTSD Scale for DSM-5 (CAPS-5; Weathers et al., 2013a).** The CAPS-5 will be used to diagnose PTSD and index PTSD symptom severity. This version of the CAPS 5 also contains a separate Criterion A assessment procedure. The CAPS-5 is closely modeled on the CAPS-IV, a structured diagnostic interview and gold standard for assessing PTSD. The CAPS-IV has excellent psychometric properties and diagnostic efficiency (Weathers, Keane, & Davidson, 2001). The CAPS-5 uses a single 4-point ordinal rating scale to measure symptom severity. These ratings combine information about symptom frequency and intensity obtained by the interviewer. CAPS-5 scores range from 0 to 80, with higher scores indicating greater PTSD symptom severity. A PTSD case will entail a rating of >2 (moderate/threshold) for the requisite DSM-5 criteria. The CAPS-5 will be administered by telephone; we have determined that distance evaluations of PTSD are reliable and valid (Litwack et al., 2014).

**Life Events Checklist (LEC; Gray, [name], Hsu, & Lombardo, 2004):** The LEC will be used to assess exposure to potentially traumatic events and will be employed in this trial to inform assessment of Criterion A for PTSD using the CAPS (described above). The LEC will be administered as an interview by the IE during the baseline assessment. The measure enquires about exposure to 17 potentially traumatic experiences (e.g., natural disasters, accidents, assaults, war zone experiences, captivity, human suffering, death, etc.) and asks participants to state whether or not they have been exposed to each event, either through directly experiencing it, witnessing it, or learning about it happening to someone close to them. In this study, participants will also be asked to clarify whether each event that they endorse happened during military service, civilian life, or both. The LEC has excellent psychometric properties (Gray, [name], Hsu, & Lombardo, 2004).

**PTSD Checklist for DSM-5 (PCL-5; Weathers et al., 2013b).** The PCL-5 will also be used to examine PTSD symptom burden. At the pre-eligibility screening, site RAs will ask veterans to write a one-sentence description of their worst and most currently distressing warzone experience on the top of the PTSD Checklist for DSM-5 (PCL-5) page and to rate symptoms referencing this event on the PCL-5. The PCL-5 will also be administered each week during therapy to track progress, capture adverse outcome, and model within-treatment change. The PCL-5 is similar to the PTSD Checklist (PCL) based on the DSM-IV. The PCL-IV has excellent psychometric characteristics (McDonald & Calhoun, 2010). The PCL-5 has 20-items which are scored in the past month on a scale from “0 = not at all” to “4 = extremely.”

Hypothesis B.5.

**Patient Health Questionnaire (PHQ-9).** This widely used and well-validated (Kroenke et al., 2001) measure will be used to measure depression. It has high internal consistency (e.g., Cameron et al., 2008) and correlates strongly with other measures of depression (Kroenke et al., 2001);

Hypothesis B.6.

**Trauma-Related Guilt Inventory (TRGI; Kubany et al., 1996).** The TRGI assesses guilty feelings and attitudes about a specific warzone event. It is scored into three scales (Global Guilt, Distress Scale, and Guilt Cognitions) and 3 subscales (Hindsight-Bias/Responsibility, Wrongdoing, and Lack of Justification).

**Trauma-Related Shame Inventory –Internal Shame Subscale (TRSI; Øktedalen et al., 2014).** The TRSI internal shame subscale is a 12-item self-report instrument designed to assess individuals' negative self-evaluations in the context of their traumatic experiences. The measure has good construct validity (Øktedalen et al., 2014).

Hypothesis B.7.

**The Schwartz Outcome Scale-10 (SOS-10; Blais et al., 1999).** Psychological health and distress will be measured using the SOS-10, a 10-item general mental health outcome measure. The SOS-10 has demonstrated good psychometric properties.

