#### **B: Mental health change hypotheses:**

- B.4.** Veterans randomized to AD-MIL will have greater reductions in PTSD symptom severity and a smaller percentage of PTSD cases
- B.5.** Veterans randomized to AD-MIL will have greater reductions in depressive symptoms
- B.6.** Veterans randomized to AD-MIL will have greater reductions in shame and guilt
- B.7.** Veterans randomized to AD-MIL will have greater reductions in psychological distress

We will also explore the impact of treatment on anger and aggressive behaviors, suicidal ideation, alcohol abuse, compassion towards self and others, and social connectedness.

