#### *Inclusionary Criteria:*

1. Age 18 or older
2. Served in an active-duty role within the military since September 2001 (Veterans may be eligible whether or not they were deployed to a warzone)
3. Meet the DSM-5 diagnostic criteria for PTSD as a result of military trauma (per Clinician Administered PTSD Scale for DSM-5 [CAPS-5]) and report non-negligible levels of associated functional impairment (Sheehan Disability Scale [SDS] score  $\geq 10$ )
4. Prospective enrollees must be willing to commit to 12 consecutive weekly therapy sessions lasting up to 90 minutes in duration and to complete assessment materials.

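### The only written PTSD case rule on the CAPS-5 contradicts its own label: as printed, a rating of 2 fails the rule, although the parenthesis most naturally names 2 as the threshold

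*Combined protocol and SAP*

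**What the plan says.** The CAPS-5 entry under Measures, section B (Hypothesis B.4) gives the instrument two jobs: "The CAPS-5 will be used to diagnose PTSD and index PTSD symptom severity". It then describes the scoring in three statements:

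- The rating scale: "The CAPS-5 uses a single 4-point ordinal rating scale to measure symptom severity".
- The total: "CAPS-5 scores range from 0 to 80, with higher scores indicating greater PTSD symptom severity".
- The case rule: "A PTSD case will entail a rating of >2 (moderate/threshold) for the requisite DSM-5 criteria".

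CAPS-5 diagnosis is used in two other places.

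- **Entry.** Item 3 of the inclusion criteria requires that a veteran "Meet the DSM-5 diagnostic criteria for PTSD as a result of military trauma", as judged on the CAPS-5. The opening of Measures adds: "Eligibility will be determined by scores on the CAPS-5". Neither place repeats an item cut-off.
- **Outcome.** Hypothesis B.4 in the Objectives predicts "greater reductions in PTSD symptom severity and a smaller percentage of PTSD cases" with AD-MIL. The Analyses section (Hypotheses 3-6) compares the case proportion between arms with a chi-square test.

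**The concern.** A threshold rating ought to satisfy the threshold. Here the number directly before the label *moderate/threshold* is 2, and the sign before that number excludes it. Two careful readers could therefore score the same interview differently: one follows the sign and needs 3 or more, the other follows the label and accepts 2.

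This matters more than an ordinary slip in a measure description because the sentence is a decision rule. It fixes who counts as a case in a named secondary outcome, and it is the only scoring rule available to anyone applying the inclusion criterion. Independent evaluators work from Boston and from all four treatment sites, so they need one unambiguous rule.

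Consistency over time is also at stake. If one reading were used at entry and the other at follow-up, a veteran whose ratings had not changed could move from case to non-case.

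**Working it through.** The plan has no stated figure to reproduce here, because the point concerns a definition. The check has four steps.

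**1. Which ratings pass.** The documents do not list the CAPS-5 anchors or the number of items, so I take each whole-number scale that could be meant.

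| Rating scale | Points | Strictly above 2 | 2 or above |
|---|---|---|---|
| 0 to 3 | 4 | 3 | 2, 3 |
| 1 to 4 | 4 | 3, 4 | 2, 3, 4 |
| 0 to 4 | 5 | 3, 4 | 2, 3, 4 |

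On every scale the two rules differ by exactly one rating, 2. The contradiction therefore does not depend on which scale is right.

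**2. Whether the scale description fits the stated total.** Let k be the number of items, and let the total be the sum of consecutive whole-number ratings.

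- 0 to 3: the maximum is 3k. Setting 3k = 80 gives k = 26.67, which is not a whole number.
- 1 to 4: the minimum is k, which is at least 1, so a total of 0 is impossible.
- 0 to 4: the minimum is 0 and the maximum is 4k. Setting 4k = 80 gives k = 20, which works.

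So neither 4-point scale can produce 0 to 80 for any number of items, while a 5-point scale with 20 items can. This mismatch does not decide between the two readings of the case rule. It does show that the paragraph needs correcting in any event, and that its exact wording is not a safe guide to intent.

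**3. Direction of the effect.** Take one fixed set of ratings. Moving from the inclusive to the strict rule can only change a symptom from present to absent. Assuming that more symptoms present never removes a diagnosis, every case under the strict rule is also a case under the inclusive rule. Hence cases(strict) ≤ cases(inclusive), with strict inequality wherever a diagnosis depends on ratings of 2. The documents give no distribution of item ratings, so the gap cannot be quantified.

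**4. What depends on the rule.**

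| Element | Uses the case rule? |
|---|---|
| Case proportion in B.4 (chi-square) | Yes, directly |
| Inclusion criterion 3 | By inference: it relies on CAPS-5 diagnosis but states no cut-off |
| CAPS-5 and PCL-5 severity slopes | The scores do not use it; only through who is enrolled |
| SDS primary endpoint | The score does not use it; only through who is enrolled |
| Sample size | No: it is built on SDS change (1.2 points, SD 2.1) |

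**The case against.** **A lost symbol.** An inclusive sign typed as an underlined *greater than* can lose its underline when a PDF is converted to text. The SDS inclusion criterion does carry an inclusive sign in the text available to us. That shows only that a true inclusive character survives; it says nothing about an underlined one. This objection stands as a real possibility. If the source prints an inclusive sign, the contradiction disappears and only the mismatch in the scale description remains.

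**No anchors.** The documents never say what each rating means, so the parenthesis might describe the whole expression rather than the number 2. That reading is less natural, and it leaves the rule ambiguous. It does mean that the documents cannot show which side should give way.

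**Trained assessors.** Assessors must match the trainer's diagnosis on three interviews, with cluster severities no more than 2 points apart, and 10% of assessments are reviewed from the recordings. This makes it less likely that one sign decides who enters the trial. It does not settle the written rule.

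**Stronger readings.** A reader might infer that remission would be overstated in both arms. The documents do not support that. With the enrolled sample and its ratings held fixed, a strict rule at follow-up cannot lower the non-case proportion. But if the strict rule also applied at entry, it would raise the severity needed to enrol, and the net direction is then undetermined. Nor is any bias between arms shown, since the rule is the same in both. A reader might also cite a veteran rated 2 on every item, who under the 20-item assumption scores 20 × 2 = 40 of 80 and is not a case. That is a constructed illustration and says nothing about how many participants would be reclassified.

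**Conclusion.** The inconsistency is real but limited. As printed, the only numeric case rule excludes the rating that its own label most naturally calls the threshold, and nothing elsewhere in the document resolves this. In size it is one rating category, 2, on any scale considered. The number of veterans affected is unknown, and so is the net effect on remission and on the treatment comparison.

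The conclusion rests on two assumptions: that the strict sign is what the source document prints, and that the parenthesis labels the number 2. The reach into eligibility is a fair inference, not a stated fact. The primary analysis keeps its definition and the trial keeps its sample size, so this is a correction to a secondary outcome definition and an entry rule, not a threat to the main result.

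**What to change.** 1. Check the source document for an inclusive sign lost in conversion.
2. If it prints the strict sign, reconcile the sign with the *moderate/threshold* label. The documents alone do not show which should change, so the sponsor must state which was intended.
3. State one explicit item-level case rule, with the rating anchors, and refer to it from inclusion criterion 3 and from the case analysis, so that the same rule applies at entry and at every follow-up.
4. Reconcile the 4-point description with the 0 to 80 range, and give the number of CAPS-5 items.
5. If any interviews have already been scored, record which rule the evaluators applied.

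The cost is a sign, a word and a sentence or two of cross-reference. No sample size, power or primary analysis figure changes. If item-level ratings are kept, the case outcome can be rescored for enrolled participants without new data collection, although entry decisions already made cannot be revisited in this way.
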